9.6.3 Laboratory Test Results

Summary statistics over time (for each protocol scheduled visit) by cohort for selected laboratory parameters (for Hematology and Clinical) as mentioned in below table.

Additional summaries may include descriptive statistics of changes from baseline over time. For laboratory urinalysis parameters a separate subject listing will be reviewed.

Table of Selected Laboratory Parameters

Hematology	Clinical Chemistry	Urinalysis
Red Blood Cells	Albumin	Bilirubin
Hemoglobin	Glucose	Blood
Hematocrit	Calcium	Glucose
Mean Corpuscular Volume	Potassium	Ketones
Platelet count	Total CO2	pH
Mean Platelet Volume	Total bilirubin	Protein
White Blood Cells	Direct bilirubin	Specific Gravity
Total neutrophils	Alkaline phosphatase (ALP)	Urobilinogen
Eosinophils	Gamma-glutamyltransferase (GGT)	
Basophils	Estimated glomerular filtration rate (eGFR)	
Lymphocytes	Blood urea nitrogen (BUN)	
Monocytes	Chloride	
	Phosphorus	
	Magnesium	
	Creatinine	
	Creatine Kinase	
	Sodium	
	Total protein	
	Aspartate aminotransferase (AST)	
	Alanine aminotransferase (ALT)	

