### 2.3 Risk Assessment

To date, AMG 529 has not been administered to human subjects; therefore, no clinical data are available. This is the first single dose study proposed in human subjects with AMG 529. The assessment of potential side effects of AMG 529 is based on the pre-clinical studies conducted to date ([Section 2.2.3](#)) and the literature.

In addition to the cardioprotective phenotype, the *ASGR1* del12 variant was associated with elevated levels of ALP (50.1% change; 95% CI, 42.9 to 57.2;  $p=3.6 \times 10^{-63}$ ) and vitamin B12 (16.6% change; 95% CI, 11.5 to 21.5;  $p=3.1 \times 10^{-12}$ ), proposed to result from reduced clearance by ASGPR ([Nioi et al, 2016](#)). Increased GGT (10.3% change; 95% CI 1.7 to 19.2;  $p=0.015$ ) and decreased albumin (-0.72 g/L; 95% CI -1.37 to 0.06;  $p=0.033$ ) were also observed, but did not reach genome-wide significance ( $p=5 \times 10^{-8}$ ). There was no association between the del12 variant and ALT (5.8% change; 95% CI -0.4 to 12.2;  $p=0.065$ ), AST (4.1% change; 95% CI -2.9 to 11.4;  $p=0.095$ ), or bilirubin (3.7% change; 95% CI -2.6 to 10.4;  $p=0.25$ ), suggesting that the increase in ALP was not likely due to underlying liver disease.

Increases in ALP and potentially GGT are expected with AMG 529 administration due to reduced clearance of these desialylated molecules from the circulation and are not indicative of hepatotoxicity. Alkaline phosphatase and GGT, along with other assessments of liver function (AST, ALT, bilirubin and albumin), will be monitored in this FIH study. The expectation is that only increases in ALP and potentially GGT will occur without clinically relevant increases in the other liver function tests.

Minimal reductions in PT were noted in the 14-day toxicology study in cynomolgus monkeys. While the clinical relevance of this finding is unclear, PT, international normalized ratio (INR), and aPTT will be evaluated in all subjects.

As with any therapeutic antibody, administration of AMG 529 may result in systemic (eg, hypersensitivity) and local (eg, injection site) reactions, and immunogenicity (ie, the development of anti-AMG 529 antibodies). A sentinel dosing strategy will thus be used

for all cohorts of this study to mitigate the chances of subjects experiencing unexpected adverse events resulting from a single dose of AMG 529.

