### **7.2.3 Treatment**

The following procedures will be completed during the treatment period at the times designated in the Schedule of Assessments ([Table 4](#) and [Table 5](#)).

- IP administration on day 1
- Vital signs (eg, blood pressure, respiratory rate, heart rate, oral temperature)
- Triplicate 12-lead ECG
- Safety laboratory assessments: clinical chemistry, hematology, coagulation, and urinalysis
- Physical examination (cohorts 3, 4 and 5)
- On-study lipid panel
- PK, anti-AMG 529 antibody, biomarker, alkaline phosphatase isoenzymes, and pharmacogenetics sample collection
- Serious Adverse Event reporting
- Adverse Event reporting
- Documentation of all concomitant medications
- In-house residency per Schedule of Assessments

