#### **7.2.5.14.2 Coagulation Tests**

The following coagulation tests will be performed: prothrombin time (PT), international normalized ratio (INR), and activated partial thromboplastin time (aPTT). The unblinded Amgen Medical Monitor will obtain, as necessary, consultation with a hematologist for changes in coagulation tests.

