## **10. STATISTICAL CONSIDERATIONS**

### **10.1 Study Endpoints, Analysis Sets, and Covariates**

#### **10.1.1 Study Endpoints**

##### **10.1.1.1 Primary Endpoints**

- Subject incidence of treatment-emergent adverse events
- Safety laboratory analytes, vital signs, and ECGs

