#### **10.5.2.1.4 Clinical Laboratory**

Analyses of laboratory values will include summary statistics over time (for each protocol scheduled visit) by cohort. Additional summaries may include descriptive statistics of changes from baseline over time.

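### SAP 9.6.3 omits PT, INR and aPTT from its closed list of laboratory parameters, so the planned end-of-study report has no coagulation output, contrary to protocol 10.5.2.1.4

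*SAP*

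**What the plan says.** SAP 9.6.3 sets the laboratory output in one sentence: "Summary statistics over time (for each protocol scheduled visit) by cohort for selected laboratory parameters (for Hematology and Clinical) as mentioned in below table". The table has three columns, headed "Hematology Clinical Chemistry Urinalysis". For the third column the SAP plans a listing and no summary: "For laboratory urinalysis parameters a separate subject listing will be reviewed". Change-from-baseline summaries are optional for every laboratory parameter.

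The protocol is broader. Its primary endpoints (10.1.1.1) include "Safety laboratory analytes, vital signs, and ECGs". Section 7.2.3 shows what the safety laboratory covers: "Safety laboratory assessments: clinical chemistry, hematology, coagulation, and urinalysis". Section 10.5.2.1.4 then plans the analysis for all of it: "Analyses of laboratory values will include summary statistics over time (for each protocol scheduled visit) by cohort". That sentence does not restrict the analytes.

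The protocol also gives a reason to look at coagulation. Section 2.3 records that "Minimal reductions in PT were noted in the 14-day toxicology study in cynomolgus monkeys", describes the clinical relevance as unclear, and commits to evaluating PT, INR and aPTT in every subject. Section 7.2.5.14.2 adds that "The unblinded Amgen Medical Monitor will obtain, as necessary, consultation with a hematologist for changes in coagulation tests". The rationale for amendment 1 lists that consultation among the changes the FDA asked for.

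SAP section 10 states that nothing departs from the analyses specified in the protocol.

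**The concern.** The SAP list is closed: a parameter is summarised if it is in the table. A programmer working from 9.6.3 would produce hematology and chemistry summaries and a urinalysis listing, and nothing for coagulation. One of the four panels that make up the safety laboratory, and so part of a primary endpoint, would drop out of the report without being declared.

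It is also the panel for which the protocol gives a specific nonclinical reason to test. Section 2.2.3 reports minimally shortened PT in some male monkeys and names coagulation proteins as ligands of the receptor that AMG 529 blocks. At stake is whether the report shows, by dose group and against placebo, what happened to PT, INR and aPTT in humans.

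**Working it through.** **1. Is coagulation anywhere in the SAP output?**

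| Panel | Protocol source | SAP 9.6.3 output |
|---|---|---|
| Hematology | Table 6 | 12 parameters, summarised |
| Clinical chemistry | Table 7 | 20 parameters, summarised |
| Urinalysis | Table 8 | subject listing |
| Coagulation (PT, INR, aPTT) | 7.2.5.14.2 | none |

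So 12 + 20 = 32 blood parameters are summarised, and 0 of the 3 coagulation tests. Elsewhere in the SAP, PT, PTT and APTT occur only in the abbreviation list. PDF extraction does not explain the gap: the governing sentence itself names only hematology and clinical parameters, and the three columns are intact.

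**2. Was it left out on purpose?** Nothing says so. SAP section 10 declares no change. The SAP is written to amendment 1, and its table includes mean platelet volume, which that amendment added to the hematology panel. Coagulation is the one panel that the protocol describes in prose and not in a table, so an oversight in transcription is plausible. That is an inference; the documents do not state it.

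**3. How much data is affected?** Inputs: collections per subject from protocol Tables 10 to 12, cohort sizes from Table 2, and visit timing from Tables 4 and 5.

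- The plan's own figures reproduce. Cohorts 1, 2 and 6: 7 draws x 2.7 mL = 18.9 mL. Cohorts 3 to 5: 8 x 2.7 mL = 21.6 mL. Both match the stated volumes.
- All scheduled draws: 24 x 7 + 24 x 8 = 168 + 192 = 360.
- Two draws per subject, at screening and day -1, precede dosing: 48 x 2 = 96.
- Post-dose draws: 24 x (7 - 2) + 24 x (8 - 2) = 120 + 144 = 264, which equals 360 - 96.
- Post-dose draws from subjects on AMG 529 (6 of 8 per cohort): 18 x 5 + 18 x 6 = 198.
- Post-dose results over three tests: 264 x 3 = 792.

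The relevant count is 264. It measures data without planned output. It does not measure bias or loss of power, since no estimate or decision rule changes.

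**4. Would other planned outputs show a PT shift?**

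- Adverse event tables: under protocol 9.2.1.1, abnormal laboratory findings without clinical significance are generally not recorded as adverse events, so an asymptomatic shift need not appear.
- Liver injury criteria (protocol 6.3.1): these use INR above 1.5, which is prolongation. The monkey change was shortening.
- SAP 9.1: the general promise of descriptive statistics is for selected safety data, and 9.6.3 makes the selection.

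**The case against.** The strongest reply is that nothing is lost. The tests are done in all subjects on a fixed schedule. Protocol 10.5.2.1.4 already commits to summarising laboratory values, and the SAP's stated purpose is to detail the protocol's analyses, with no change declared. On that reading the protocol summary still stands and the SAP table is merely incomplete. This is partly right: it makes the problem an inconsistency between two documents and not a cancelled analysis. But the SAP is the document that specifies the output, and its list is closed, so the inconsistency needs resolving.

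A reader might go further and infer that the trial could not tell whether the monkey effect occurs in humans. The documents do not support that. The data will exist and can be summarised whenever the SAP is corrected.

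A reader might also infer that subjects are less well protected. That does not follow either. Safety laboratory results go to each dose level review meeting (protocol 6.2.1.2.1). The unblinded medical monitor reviews data throughout and may suspend dosing (6.2.1.2.2), and obtains hematology advice as needed. The investigator judges each laboratory result against the subject's baseline (9.2.1.1). None of this replaces a reported comparison by dose, but it does confine the gap to reporting.

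Finally, the nonclinical finding should not be inflated. Protocol 2.2.3 calls the PT shortening minimal, limits it to some males, and judges it non-adverse on low incidence, small magnitude and no clinical or histological sign of thrombosis. No INR effect is reported, and aPTT is mentioned only as not prolonged.

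**Conclusion.** The point holds as an undeclared conflict between the SAP and the protocol. SAP 9.6.3 gives no summary or listing for PT, INR or aPTT. Protocol 10.5.2.1.4, the primary endpoint and SAP section 10 together imply that they should be summarised. The size is 0 of 3 coagulation tests and 264 scheduled post-dose draws with no planned output.

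The count assumes 48 subjects, all visits completed, and no unscheduled or repeat tests. The conclusion that output would be missing assumes that the SAP list is followed literally.

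This is more than missing detail, because the omitted panel is the one the protocol undertakes to evaluate on account of a nonclinical finding. It does not show lost data, weakened oversight during the study, or an adverse coagulation effect in monkeys.

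**What to change.** Add a Coagulation column (PT, INR, aPTT) to the SAP 9.6.3 table and name coagulation in the governing sentence. The three tests are then summarised by visit and cohort, with placebo pooled across cohorts as SAP 9.1 provides for data other than adverse events. If the omission was intended, declare and justify it in SAP section 10.

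Two additions are recommended but optional, since the plan requires neither for any other laboratory analyte:

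- change from baseline by visit, cohort and pooled placebo;
- counts of values below and above the reference range. The direction of interest is shortening, and exclusion criterion 209 requires PT and aPTT within range at screening and day -1, so a later value below range would be easy to interpret.

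The cost is SAP wording and one table set. No new sampling or protocol change is needed, provided the change is made before database lock.

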### 6.3.1 Criteria for Permanent Withholding of Amgen Investigational Product and Other Protocol-required Therapies Due to Potential Hepatotoxicity

Following the single-dose administration of study drug, the subject should be followed according to the recommendations in [Appendix A](#) (Additional Safety Assessment Information) for possible drug-induced liver injury (DILI), if ALL of the criteria below are met:

- TBL > 2x upper limit of normal (ULN) or INR > 1.5
- AND increased AST or ALT from the relevant baseline value as specified below:

Baseline AST or ALT value	AST or ALT elevation
< ULN	≥ 3x ULN

- AND no other cause for the combination of the above laboratory abnormalities is immediately apparent; important alternative causes for elevated AST/ALT and/or TBL values include, but are not limited to:
  - Hepatobiliary tract disease
  - Viral hepatitis (eg, Hepatitis A/B/C/D/E, Epstein-Barr Virus, cytomegalovirus, Herpes Simplex Virus, Varicella, toxoplasmosis, and Parvovirus)
  - Right sided heart failure, hypotension or any cause of hypoxia to the liver causing ischemia.
  - Exposure to hepatotoxic agents/drugs or hepatotoxins, including herbal and dietary supplements, plants and mushrooms
  - Heritable disorders causing impaired glucuronidation (eg, Gilbert's Syndrome, Crigler-Najjar syndrome) and drugs that inhibit bilirubin glucuronidation (eg, indinavir, atazanavir)
  - Alpha-one antitrypsin deficiency
  - Alcoholic hepatitis
  - Autoimmune hepatitis
  - Wilson's disease and hemochromatosis
  - Nonalcoholic Fatty Liver Disease including Steatohepatitis (NASH)
  - Non-hepatic causes (eg, rhabdomyolysis, hemolysis)

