#### **Additional Clinical Assessments and Observation**

All subjects in whom investigational product(s) or protocol-required therapies is/are withheld (either permanently or conditionally) due to potential DILI as specified in [Section 6.3.1](#) or who experience AST or ALT elevations > 3 x ULN or 2-fold increase above baseline values for subjects with evaluated values before drug are to undergo a period of “close observation” until abnormalities return to normal or to the subject’s baseline levels. Assessments that are to be performed during this period include:

- Repeat AST, ALT, ALP, bilirubin (total and direct), and INR within 24 hours
- In cases of TBL > 2x ULN or INR > 1.5, retesting of liver tests, BIL (total and direct), and INR is to be performed every 24 hours until laboratory abnormalities improve
- Testing frequency of the above laboratory tests may decrease if the abnormalities stabilize or the investigational product(s) or protocol-required therapies has/have been discontinued AND the subject is asymptomatic.
- Initiate investigation of alternative causes for elevated AST or ALT and/or elevated TBL. The following are to be considered depending on the clinical situation:
  - Complete blood count (CBC) with differential to assess for eosinophilia
  - Serum total immunoglobulin IgG, Anti-nuclear antibody (ANA), Anti Smooth Muscle Antibody, and Liver Kidney Microsomal antibody 1 (LKM1) to assess for autoimmune hepatitis
  - Serum acetaminophen (paracetamol) levels
  - A more detailed history of:
    - Prior and/or concurrent diseases or illness
    - Exposure to environmental and/or industrial chemical agents

- Symptoms (if applicable) including right upper quadrant pain, hypersensitivity-type reactions, fatigue, nausea, vomiting and fever
  - Prior and/or concurrent use of alcohol, recreational drugs and special diets
  - Concomitant use of medications (including non-prescription medicines and herbal and dietary supplements), plants, and mushrooms
- Viral serologies
- CPK, haptoglobin, LDH, and peripheral blood smear
- Appropriate liver imaging if clinically indicated
- Appropriate blood sampling for pharmacokinetic analysis if this has not already been collected
- Hepatology consult (liver biopsy may be considered in consultation with an hepatologist)

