9.1 General Considerations

Descriptive statistics will be provided for selected demographics, safety, PK, and PD data. Data for subjects receiving placebo will be combined across all cohorts, except for adverse events where the combined SC cohorts will be summarized separately from the IV cohort. Descriptive statistics on continuous measurements will include means, medians, standard deviations, and ranges, while categorical data will be summarized using frequency counts and percentages. Data will be summarized by treatment group and at each time point when samples are collected. The number and percent of subjects reporting any treatment-emergent adverse events will be tabulated by system organ class and preferred term and will be further classified by relationship to treatment.

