9.6.5 Electrocardiogram

All on-study ECG data will be reviewed and may be plotted.

Each ECG will include the following measurements: QRS, QT, QTc, RR, and PR intervals. The Fridericia's (QTcF) QT correction will be computed as specified in [section 5](#). All ECG parameters will be summarized over time and change from baseline over time will be provided. Further, subjects' maximum change from baseline in QTcF will be categorized in following categories and the number and percentage of subjects in each group will be summarized. Unscheduled assessments will be included in the determination of the maximum change.

- ≤ 30 msec
- > 30 – 60 msec
- > 60 msec

Subjects' maximum post baseline values in QTcF and QTcB will also be categorized in the following categories and the number and percentage of subjects in each group will be summarized.

- ≤ 450 msec
- > 450 – 480 msec
- > 480 – 500 msec
- > 500 msec

The number of subjects in each group will be summarized for each cohort. Baseline ECG recording is defined as the mean of the 3 sets of triplicate ECG results at study day 1 pre-dose (a total of 9 assessments).

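### The SAP plans no worst-value, × ULN or within-subject summary of liver tests, so an isolated AST/ALT rise above 3 × ULN or a peak on an unscheduled retest is not assured a place in the reported results

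*SAP*

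**What the plan says.** Protocol 10.5.2.1.4 gives one rule for laboratory data: "Analyses of laboratory values will include summary statistics over time (for each protocol scheduled visit) by cohort". SAP 9.6.3 narrows it to a list of selected parameters: "Summary statistics over time (for each protocol scheduled visit) by cohort for selected laboratory parameters". The only addition is optional: "Additional summaries may include descriptive statistics of changes from baseline over time". SAP 9.1 names the statistics: "Descriptive statistics on continuous measurements will include means, medians, standard deviations, and ranges". A subject listing is mentioned for urinalysis only. PT, INR and aPTT are scheduled in protocol Tables 4 and 5 but do not appear in the SAP's parameter table.

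Protocol 6.3.1 defines possible drug-induced liver injury within one subject. It requires "TBL > 2x upper limit of normal (ULN) or INR > 1.5", together with "AND increased AST or ALT from the relevant baseline value as specified below" (at least 3 × ULN when baseline is below ULN), and no other cause immediately apparent. Protocol Appendix A starts close observation when AST or ALT exceeds 3 × ULN, with a repeat within 24 hours. Where bilirubin or INR passes its limit, "retesting of liver tests, BIL (total and direct), and INR is to be performed every 24 hours until laboratory abnormalities improve".

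For ECGs, SAP 9.6.5 works per subject. It categorises each subject's maximum QTcF change and maximum post-baseline value, and for the maximum change it states: "Unscheduled assessments will be included in the determination of the maximum change".

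**The concern.** The protocol judges liver safety by subject, in multiples of ULN, and jointly across analytes. The planned tables work by analyte, by visit and by cohort. They contain no count of subjects above a threshold and no link between one subject's ALT and that subject's bilirubin or INR. They also give no place to a value drawn between scheduled visits.

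Protocol 2.3 expects ALP, and possibly GGT, to rise without clinically relevant change in the other liver tests. A reader of the study report will want to know how many treated and placebo subjects crossed the protocol's own limits. The committed outputs do not answer that directly, although the data to answer it are collected.

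**Working it through.** **1. The plan's own figures.** The sample-size text rests on seeing at least one affected subject, P = 1 − (1 − p)^n.
- n = 6, p = 0.20: 1 − 0.80^6 = 0.738; stated 74%, reproduced.
- n = 36, p = 0.05: 1 − 0.95^36 = 0.842; stated 84%, reproduced.

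Nothing here changes these figures. They do show that the study's safety logic is a count of affected subjects, which the chemistry tables lack.

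**2. Which results the rule covers.** After removing the ALP-only days (3, 6, 8, 15 and, in cohorts 3 to 5, 43), post-dose AST, ALT and bilirubin are scheduled on Days 2, 4, 11, 22 and 30, plus Day 57 in cohorts 3 to 5. The intervals are 2, 7, 11, 8 and 27 days. The Appendix A retests are in neither Table 4 nor Table 5, so they are not protocol-scheduled visits. The intervals show where retests can fall; they are a matter of sampling, and the fix does not alter them.

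**3. Who is covered by other routes.**

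| Pattern | Retests (protocol Appendix A) | SAE report and narrative |
|---|---|---|
| AST/ALT at least 3 × ULN, with bilirubin > 2 × ULN or INR > 1.5, no other cause apparent | Within 24 hours, then every 24 hours | Yes |
| Same combination with AST/ALT > 3 × ULN, other cause immediately apparent | Within 24 hours, then every 24 hours | Only if serious on other grounds |
| AST/ALT > 3 × ULN, bilirubin and INR within limits | One repeat within 24 hours assured | Not automatic |

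The third row is the main gap. Under protocol 9.2.1.1, an abnormal value that the investigator judges not clinically significant is generally not recorded as an adverse event.

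**4. What by-visit statistics show (assumed values).** Take a 6-subject arm with five subjects at 0.5 × ULN.
- Sixth at 3: mean = (5 × 0.5 + 3)/6 = 0.92; median 0.5. With the five at 0.4 to 0.7, the mean is 0.83 to 1.08.
- Sixth at 5: mean = (2.5 + 5)/6 = 1.25; median 0.5. With the five at 0.4 to 0.7, the mean is 1.17 to 1.42.
- Sixth at 5 on the scheduled day and 8 on the retest: the table still gives mean 1.25 and maximum 5. With the peak counted, these would be (2.5 + 8)/6 = 1.75 and 8.

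**5. If the rise is recorded as an adverse event.** SAP 9.6.2 drops adverse-event tables when no more than two subjects in the study have the event. If that is applied event by event, with 36 treated subjects and placebo cases ignored, P(1 or 2 cases) = 36p(1 − p)^35 + 630p²(1 − p)^34.
- p = 0.05: 0.299 + 0.275 = 0.574, which is 0.574/0.842 = 68% of trials with any case.
- p = 0.02: 0.482 (93%). p = 0.10: 0.265 (27%).

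The incidences are assumptions. If the rule instead suppresses only whole tables, such an event would still appear in the overall table, provided more than two subjects had any event.

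**6. INR.** The protocol's general rule would take in coagulation results. The SAP's table omits them, although SAP section 10 says that protocol-specified analyses are unchanged. The INR part of 6.3.1 is therefore not committed to a summary even by visit.

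**The case against.** A reader might infer that the 24-hourly results taken during a liver injury disappear from the report. The documents do not support that. The 24-hourly rule applies only when bilirubin or INR passes its limit. A subject with raised AST/ALT as well will generally meet 6.3.1. Protocol Appendix A then requires an SAE report within 24 hours and CRF capture of the laboratory results, and SAP 9.6.2 provides narratives for serious treatment-emergent events. Such results are outside the by-visit summaries, but they are not lost.

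Other points also stand:
- The range will show a peak that falls on a scheduled day, so the dilution of a mean is a weak argument on its own.
- ALP also has a repeated-measures model (SAP 9.7.1.2).
- Differences between local reference ranges are only possible; the study may run at a single site.
- The unblinded medical monitor and the dose level review meetings watch safety during conduct.
- The study is descriptive, and the expectation in protocol 2.3 is not one of its stated hypotheses.

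Two replies remain. Monitoring during conduct is not the reported analysis. And although SAP 9.1 speaks of summarising at every time point with samples, 9.6.3 is the specific laboratory rule and is narrower.

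**Conclusion.** The point holds in limited form. For AST, ALT and total bilirubin, the plan commits only to per-analyte statistics at scheduled visits, and for PT, INR and aPTT the SAP commits to none. An isolated AST/ALT rise above 3 × ULN is not identified as such in any planned table and is assured no narrative. A retest peak outside the 6.3.1 cases has no assured place either. Joint elevation in one subject cannot be read from separate ranges.

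The broader inference, that drug-induced liver injury meeting the protocol's criteria would go unreported, does not hold. The size is presentational: no effect on the 48 subjects, the assessments or the 74% and 84% figures. How often it would matter depends on the unknown incidence of isolated elevations, on investigators' judgement of clinical significance, and on how the two-subject rule is read. I would class it as a cheap improvement to a primary-endpoint analysis.

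**What to change.** In SAP 9.6.3:
- Add one table by treatment group, with placebo pooled. It gives each subject's worst post-baseline AST, ALT and total bilirubin in multiples of the reporting laboratory's ULN, and worst INR. Include unscheduled and retest values, and categorise at the protocol's own thresholds.
- Add a count and a listing of subjects who meet the joint 6.3.1 laboratory criteria.
- Add PT, INR and aPTT to the selected-parameter table.
- Keep the by-visit summaries as they are.

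Before the category boundary is set, the sponsor must reconcile the AST/ALT limit in protocol 6.3.1 (at least 3 × ULN) with that in protocol Appendix A (above 3 × ULN). The sponsor should also state how the joint count treats a subject whose baseline is not below ULN, since 6.3.1 gives a limit only for baselines below it and exclusion criterion 208 allows values up to 1.1 × ULN.

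The cost is one SAP paragraph, a little programming, and a check that laboratory reference ranges are in the database, which neither document states. No new sample or visit is needed.
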